9.0 STATISTICAL CONSIDERATIONS

9.1 Statistical Hypotheses

No formal statistical hypotheses are to be tested.

9.2 Sample Size Determination

This study is a Phase I safety study to get preliminary safety and immunogenicity assessments of vaccine formulations in adults.

The target will be to enroll a maximum of 140 healthy subjects (approximately 20 subjects aged 18-45 years in Step 1, approximately 20 subjects aged 50-70 years in Step 2, approximately 30 subjects aged 50-70 years in Step 3, and approximately 70 subjects aged 50-70 years in Step 4 [refer to [Table 10](#) and [Figure 1](#)]) (refer to Section [8.11](#) for study procedures to be considered during special circumstances).

The sample size of 45 subjects aged 50-70 years in each active arm (CDIFF Ag or CDIFF Ag + AS01_B) would provide a probability of 80% or 90% to observe at least 1 specific AE, if the true AE rate is 3.5% or 5.0%, respectively, in that group.

[Table 22](#) illustrates the precision on the percentage of subjects with symptoms following vaccination with 45 subjects vaccinated in each active arm.

Table 22 95% Confidence Interval for 1 Proportion with 45 Subjects

Number of Subjects with a Symptom	Percentage	Exact 95% Confidence Interval	
		Lower Limit	Upper Limit
0	0.0%	0.0%	7.9%
1	2.2%	0.1%	11.8%
2	4.4%	0.5%	15.1%
3	6.7%	1.4%	18.3%
4	8.9%	2.5%	21.2%
5	11.1%	3.7%	24.1%
6	13.3%	5.1%	26.8%
7	15.6%	6.5%	29.5%
8	17.8%	8.0%	32.1%
9	20.0%	9.6%	34.6%
10	22.2%	11.2%	37.1%
11	24.4%	12.9%	39.5%
12	26.7%	14.6%	41.9%

Table 22 95% Confidence Interval for 1 Proportion with 45 Subjects

Number of Subjects with a Symptom	Percentage	Exact 95% Confidence Interval	
		Lower Limit	Upper Limit
13	28.9%	16.4%	44.3%
14	31.1%	18.2%	46.6%
15	33.3%	20.0%	49.0%
16	35.6%	21.9%	51.2%
17	37.8%	23.8%	53.5%
18	40.0%	25.7%	55.7%
19	42.2%	27.7%	57.8%
20	44.4%	29.6%	60.0%
21	46.7%	31.7%	62.1%
22	48.9%	33.7%	64.2%
23	51.1%	35.8%	66.3%
24	53.3%	37.9%	68.3%
25	55.6%	40.0%	70.4%
26	57.8%	42.2%	72.3%
27	60.0%	44.3%	74.3%
28	62.2%	46.5%	76.2%
29	64.4%	48.8%	78.1%
30	66.7%	51.0%	80.0%
31	68.9%	53.4%	81.8%
32	71.1%	55.7%	83.6%
33	73.3%	58.1%	85.4%
34	75.6%	60.5%	87.1%
35	77.8%	62.9%	88.8%
36	80.0%	65.4%	90.4%
37	82.2%	67.9%	92.0%
38	84.4%	70.5%	93.5%
39	86.7%	73.2%	94.9%
40	88.9%	75.9%	96.3%
41	91.1%	78.8%	97.5%
42	93.3%	81.7%	98.6%
43	95.6%	84.9%	99.5%
44	97.8%	88.2%	99.9%

Table 22 95% Confidence Interval for 1 Proportion with 45 Subjects

Number of Subjects with a Symptom	Percentage	Exact 95% Confidence Interval	
		Lower Limit	Upper Limit
45	100.0%	92.1%	100.0%

Exact 95% confidence interval computed based on Clopper-Pearson formula.

Although key assumptions using GSK tests are not available at this stage, the variability values used in the statistical computations have been derived from the clinical data published by Sheldon (2016).¹⁷ The standard deviation (SD) log10 value of 0.84 and 1.4 have been used in the statistical calculations of the precision around the geometric mean fold-rise (GMFR) from prevaccination to postvaccination, respectively, for Toxin A and Toxin B.¹⁷

Assuming 20% of nonevaluable subjects, 36 older adults in each active arm (CDIFF Ag or CDIFF Ag + AS01_B) will be evaluable and included in the Per-protocol Set for analysis of immunogenicity. **Table 23** illustrates the 95% confidence interval (CI) for various values of GMFR for Toxin A and Toxin B.

Table 23 95% Confidence Intervals Based on Variability Assumptions of 0.84-fold for Anti-Toxin A and 1.4-fold for Anti-Toxin B and on a Sample Size Including 36 Evaluable Subjects

Observed GMFR value	Toxin A	Toxin B
10	[5.20; 19.23]	[3.36; 29.79]
15	[7.80; 28.85]	[5.04; 44.68]
20	[10.40; 38.46]	[6.715; 59.57]
30	[15.60; 57.69]	[10.07; 89.36]
40	[20.80; 76.92]	[13.43; 119.14]
50	[26.00; 96.15]	[16.79; 148.93]

GMFR = geometric mean fold-rise.

Thirty subjects aged 50-70 years will be enrolled in the placebo group as control for safety.

Ten additional subjects aged 18-45 years receiving CDIFF Ag and 10 subjects aged 18-45 years receiving placebo will be enrolled to evaluate safety and reactogenicity of the *C. difficile* F2 fusion protein in young and healthy adults during the Step 1 of the staggered design (refer to **Figure 1**).

A total of 120 subjects aged 50-70 years (30 receiving placebo, 45 receiving CDIFF Ag, and 45 receiving CDIFF Ag + AS01_B) and 20 subjects aged 18-45 years (10 receiving placebo and 10 receiving CDIFF Ag) will be enrolled in this study.

9.3 Populations for Analyses

For purposes of analysis, the analysis sets in [Table 24](#) are defined.

Table 24 Analysis Sets

Analysis Set	Description
Enrolled Set	All subjects who signed the ICF.
Exposed Set	
All subjects who have received at least 1 dose of the study vaccine. The allocation in a group is done in function of the administered treatment.
 
 Unsolicited Safety Set Solicited Safety Set Subcohort Exposed Set
Full analysis Set	All subjects who received at least 1 dose of the study treatment and have postvaccination immunogenicity data.
Per-protocol Set	
All subjects who received at least 1 dose of the study treatment to which they are randomized and have postvaccination data (Full Analysis Set) minus subjects with protocol deviations that lead to exclusion. The protocol deviations leading to exclusion of the subjects will be detailed in the SAP.
 
Three Per-protocol Sets for analysis of immunogenicity will be derived.
 
 Per-protocol Set for analysis of immunogenicity at Day 61 (1-month post dose 2) Per-protocol Set for analysis of immunogenicity at Day 180 Per-protocol Set for analysis of immunogenicity at Day 390
Subcohort Per-protocol Set	
 Subcohort Per-protocol Set for analysis of immunogenicity at Day 521 in the Subcohort Set Subcohort Per-protocol Set for analysis of immunogenicity at Day 670 in the Subcohort set

AE = adverse event; ICF = informed consent form; SAP = statistical analysis plan

9.4 Statistical Analyses

9.4.1 Analysis of Demographics

Demographic characteristics (age at first study vaccination in years, gender, and ethnicity), cohort description, withdrawal status will be summarized by group using descriptive statistics:

- Frequency tables will be generated for categorical variable such as gender.
- Mean, median, and SD will be provided for continuous data such as age.

9.4.2 Safety Analyses

9.4.2.1 Primary Analyses

The primary analysis will be performed on the Exposed Set.

The percentage of subjects with at least 1 local AE (solicited and unsolicited), with at least 1 general AE (solicited and unsolicited) and with any AE during the 7-day or the 30-day follow-up period will be tabulated with exact 95% CI after each vaccination and overall. The percentage of doses followed by at least 1 local AE (solicited and unsolicited), by at least 1 general AE (solicited and unsolicited) and by any AE will be tabulated, overall vaccination course, with exact 95% CI. The same computations will be done for Grade 3, any AEs considered related to vaccination and any Grade 3 AEs considered related to vaccination.

The percentage of subjects/doses reporting each individual solicited local and general AE during the 7-day follow-up period will be tabulated with exact 95% CI as follows:

- Over the 2 or 3 doses, the percentage of subjects with the symptom and its exact 95% CI.
- Over the 2 or 3 doses, the percentage of doses with the symptom and its exact 95% CI.
- At each study dose (visit), the percentage of subjects with the symptom and its exact 95% CI.

Occurrence of fever will be reported per 0.5°C cumulative increments as from $\geq 38^{\circ}\text{C}$ as well as the occurrence of fever $>40^{\circ}\text{C}/104^{\circ}\text{F}$ with causal relationship to the study treatment.

The verbatim reports of unsolicited symptoms will be reviewed by a physician and the signs and symptoms will be coded according to the Medical Dictionary for Regulatory Activities (MedDRA). Every verbatim term will be matched with the appropriate preferred term. The percentage of subjects with unsolicited AEs within 30 days after any doses with its exact 95% CI will be tabulated by group and by MedDRA preferred term. Similar tabulation will be done for Grade 3 unsolicited AEs, for unsolicited AEs that resulted in a medically attended visit, for Grade 3 and causally related unsolicited AEs and for unsolicited AEs causally related to vaccination.

The number of subjects who experienced at least 1 SAE or any AE of specific interest (pIMD) during the entire study period will be reported.

For each group and for each hematology, biochemistry, and urinalysis parameter:

- The percentage of subjects having hematology, biochemistry, and urinalysis results below or above the local laboratory normal ranges will be tabulated by timepoint.
- The maximum grading from Screening up to Visit 5 (Day 61)/Visit 7 (Day 390) for subjects receiving 2 doses/Visit 11 (Day 670) for subjects receiving a third dose will be tabulated (grades will be based on local laboratory normal ranges and derived from Food and Drug Administration [FDA] Guidance to Industry “Toxicity Grading Scale for Healthy Adult and Adolescent Volunteers Enrolled in Preventive Vaccine Clinical Trials” [refer to [Table 13](#)]). Those laboratory parameters not included in the FDA grading scale will not be graded).

The percentage of subjects using concomitant medication (any medication, any antipyretic and any antipyretic taken prophylactically, respectively) during the 7-day follow-up period and during the 30-day follow-up period will be summarized by group after each vaccination and overall.

Separate safety summaries for Subcohort Set may be generated as appropriate.

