4.2.2 Rationale for Randomization and the Use of Placebo

Randomized, placebo-controlled studies are widely considered to be the most rigorous method for the efficacy evaluation of treatments or prevention interventions. To be ethical, clinical

research requires balancing rigorous science with the protection of subjects. The use of placebo controls in studies for conditions with no effective treatment is widely accepted.⁶ Up to date, there is no established standard of care to prevent CDI.

Likewise, the Declaration of Helsinki allows placebo controls and states: “Where for compelling and scientifically sound methodological reasons the use of placebo is necessary to determine the efficacy or safety of an intervention and the patients who receive placebo will not be subjected to additional risks of serious or irreversible harm.”⁷

Randomization is used to reduce bias of selection and the placebo group is included as a control for the reactogenicity, the safety and the immunogenicity assessments.

The third dose of the vaccine is being given to the subjects recruited in the active groups of the last step of the study, to demonstrate if a similar kinetics in terms of anti-Toxin A/Toxin B can be achieved with the F2 antigen formulation with or without an adjuvant. Therefore, the third dose will not be given to the subjects receiving placebo.

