### 16.1. ADVERSE EVENTS

Adverse Events (AEs) will be coded using Medical Dictionary for Regulatory Activities (MedDRA) central

---

Document:	\\usadc-nas01a\cp_ops\PROJECTS\Glaxo SmithKline\GSK208109_BZA47109\SAP		
Author:	PPD [REDACTED]	Version Number:	3.0
		Version Date:	27SEP2021

Template No: CS\_TP\_BS016 – Revision 5  
Effective Date: 01Apr2018

Reference: CS\_WI\_BS005

---

coding dictionary, Version 22.0.

The percentage of subjects with at least 1 local AE (solicited and unsolicited), with at least 1 general AE (solicited and unsolicited) and with any AE during the 7-day or the 30-day follow-up period will be tabulated with exact 95% CI after each vaccination and overall.

The percentage of doses followed by at least 1 local AE (solicited and unsolicited), by at least 1 general AE (solicited and unsolicited) and by any AE will be tabulated, overall vaccination course, with exact 95% CI. The same computations will be done for Grade 3, any AEs considered related to vaccination, any Grade 3 AEs considered related to vaccination and any AEs resulting in a medically attended visit.

The percentage of subjects/doses reporting each individual solicited local and general AE during the 7-day follow-up period will be tabulated with exact 95% CI as follows:

- Over the 2 or 3 doses, the percentage of subjects with the symptom and its exact 95% CI.
- Over the 2 or 3 doses, the percentage of doses with the symptom and its exact 95% CI.
- At each study dose (visit), the percentage of subjects with the symptom and its exact 95% CI.

Occurrence of fever will be reported per 0.5°C cumulative increments as from  $\geq 38^{\circ}\text{C}$  as well as the occurrence of fever  $>40^{\circ}\text{C}/104^{\circ}\text{F}$  with causal relationship to the study treatment.

The verbatim reports of unsolicited symptoms will be reviewed by a physician and the signs and symptoms will be coded per the Medical Dictionary for Regulatory Activities (MedDRA). Every verbatim term will be matched with the appropriate preferred term. The percentage of subjects with unsolicited AEs within 30 days after any doses with its exact 95% CI will be tabulated by group and by MedDRA preferred term. Similar tabulation will be done for Grade 3 unsolicited AEs, for unsolicited AEs that resulted in a medically attended visit, for Grade 3 and causally related unsolicited AEs and for unsolicited AEs causally related to vaccination. These tabulations will include SOC and SOC/PT analyses.

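### In the 50–70 year groups, cumulative per-subject AE rows set two reporting windows on placebo beside up to three on active vaccine, with no two-dose row specified for the later tables

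*Protocol*

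**What the plan says.** Protocol 9.4.2.1 bases the safety analysis on everyone who received a dose: "The primary analysis will be performed on the Exposed Set". For each solicited symptom it lists three rows, and SAP 16.1 repeats them. The first is cumulative for each subject: "Over the 2 or 3 doses, the percentage of subjects with the symptom and its exact 95% CI". The second also runs across the whole course but takes doses, not subjects, as its denominator. The third returns to subjects and is shown separately for every vaccination.

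For unsolicited events, SAP 16.1 tabulates "The percentage of subjects with unsolicited AEs within 30 days after any doses with its exact 95% CI", and the protocol does the same by group. Local, general and any-AE percentages are given after each vaccination and overall. So are the concomitant-medication percentages (Protocol 9.4.2.1, SAP 13).

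SAP 6.2 sets out the reporting columns by age group and treatment, without a split by number of doses received. Protocol 4.1 restricts Dose 3 to Step 4 subjects on active vaccine, and Protocol 4.2.2 states that "the third dose will not be given to the subjects receiving placebo". SAP 5.2.3 defines a Subcohort Exposed Set, but SAP 16.1 does not use it. On Dose 3 safety tables, Protocol 9.4.2.1 says only: "Separate safety summaries for Subcohort Set may be generated as appropriate".

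**The concern.** A subject counts as positive in a cumulative row if the event follows any dose received. A further dose can therefore add subjects to the numerator but never remove any. Only active subjects can receive the further dose, and they are pooled in one column with active subjects from Steps 2 and 3 who received two.

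Protocol 4.2.2 names placebo as the control for reactogenicity and safety. In these rows, a difference from placebo combines any vaccine effect with an additional opportunity to report. The two active columns are also unequal, because a larger share of the adjuvanted group can receive Dose 3. The contrast between formulations is shifted in the same way. Protocol 4.3 expects reactogenicity to rise after Dose 2 or Dose 3 of an adjuvanted vaccine, so the pooled row describes neither a two-dose nor a three-dose course.

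**Working it through.** **The plan's own figure.** The documents give no expected value for these rows and no background symptom rate. The nearest figure is in Protocol 9.2: the chance of seeing at least one AE among 45 subjects, stated as 80% and 90% at true rates of 3.5% and 5.0%. The formula 1 − (1 − p)^45 gives 79.9% and 90.1%, so it reproduces. The check below uses the same at-least-one formula, with windows in place of subjects.

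**Inputs from the documents.**
- 50–70 year groups: 30 placebo, 45 CDIFF Ag, 45 CDIFF Ag + AS01B (Protocol 9.2).
- Step 4 active subjects: 25 Ag and 35 Ag + AS01B (Protocol Table 10). The largest possible Dose 3 share f is 25/45 = 55.6% and 35/45 = 77.8%.
- Mean windows per subject at full uptake: placebo 2.00; Ag 2 + 25/45 = 2.56; Ag + AS01B 2 + 35/45 = 2.78.
- Protocol Table 21 expects about 60 subjects at Visit 8 and about 50 at Visits 10 and 11. The split by arm is not given. Assuming it is proportional, both shares are multiplied by 5/6.

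**Assumptions.** The per-window probability p is the same in every arm and at every dose (no vaccine effect). Windows are first taken as independent.

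**Formulas.**
- Placebo: 1 − (1 − p)²
- Active: 1 − (1 − p)² + f·p(1 − p)²
- Spurious excess: f·p(1 − p)², largest at p = 1/3

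At p = 10%, p(1 − p)² = 0.1 × 0.81 = 8.1 points. Then 8.1 × 25/45 = 4.5 and 8.1 × 35/45 = 6.3.

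| p per dose | Placebo, two doses | Excess Ag / Ag + AS01B, all 60 given Dose 3 | Excess, about 50 given Dose 3 |
|---|---|---|---|
| 2% | 4.0% | 1.1 / 1.5 | 0.9 / 1.2 |
| 5% | 9.8% | 2.5 / 3.5 | 2.1 / 2.9 |
| 10% | 19.0% | 4.5 / 6.3 | 3.8 / 5.3 |
| 20% | 36.0% | 7.1 / 10.0 | 5.9 / 8.3 |
| 33% | 55.6% | 8.2 / 11.5 | 6.9 / 9.6 |
| 50% | 75.0% | 6.9 / 9.7 | 5.8 / 8.1 |

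**Within-subject correlation.** With a beta-binomial model, a = p(1/ρ − 1) and b = (1 − p)(1/ρ − 1), and the chance of no event in k windows is the product of (b + i)/(a + b + i) for i = 0 to k − 1. At p = 20% and full uptake, the excess falls from 7.1 / 10.0 points to 4.1 / 5.8 at ρ = 0.3, 2.0 / 2.9 at ρ = 0.6 and 0.5 / 0.6 at ρ = 0.9.

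**Between the active columns.** The unequal Dose 3 share adds (10/45)·p(1 − p)² to Ag + AS01B relative to Ag. Under independence this is at most 3.3 points.

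**Rows not inflated.** Under the same no-effect model, the percentage of doses has expectation p in every arm, and so does each single-dose row. A row limited to Doses 1 and 2 has expectation 1 − (1 − p)² in every arm, for example 19.0% at p = 10%.

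**The case against.** A reader might infer that the reactogenicity comparison with placebo is lost, or that the primary endpoint is biased as a whole. The documents do not support that. The solicited and unsolicited endpoints in Protocol 3.0 are defined after each vaccination. The at-each-dose rows answer them with one window per subject and stand beside the cumulative row. The percentage-of-doses row is not raised by the extra window either.

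A reader might also infer that no two-dose overall table will ever exist. That goes too far. The first interim analysis covers data to Day 61, and Amendment 03 introduced Dose 3 after interim results in two-dose recipients, so its overall rows cover two doses in every arm. Protocol 9.8 and SAP 4.4 have all previous analyses re-produced at the end.

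Other points also stand. Safety is descriptive, with no between-group testing (SAP 16), so no error rate changes. Rates of 20–50% lie around the peak of the curve, whereas Grade 3 rows and single preferred terms may well be at a few percent. Dose 3 recipients must have completed their visits and still be eligible, which could lower their reporting further. Table shells were not supplied, and SAP 6.2 describes its columns only as the general presentation, so the final layout cannot be confirmed.

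What remains is a gap in specification. Neither Protocol 9.4.2.1 nor SAP 16.1 names a Doses 1 and 2 row, and no dose cut-off is stated for the re-produced safety tables. SAP 4.3 limits interim safety tables to the Exposed Set, so the second interim would show the mixed rows. Descriptive percentages with confidence intervals are the main output of the primary objective, so unequal exposure in them matters without a test.

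**Conclusion.** The point holds for the cumulative per-subject rows in the 50–70 year groups; the 18–45 year groups receive no third dose. With no vaccine effect, independent windows and full Dose 3 uptake, the active columns exceed placebo by about 2.5 points (Ag) and 3.5 points (Ag + AS01B) at 5% per dose and by 4.5 and 6.3 points at 10%. The maximum is 8.2 and 11.5 points near 33%. The excess is smaller with about 50 of 60 treated and falls towards zero if the same subjects react each time. The per-dose rates and the correlation are assumptions, because the documents give neither.

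The rows at each dose and per dose given are sound as planned. The plan should be changed because the correction is cheap and the affected rows are easily read as a comparison with placebo.

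**What to change.** In Protocol 9.4.2.1 and SAP 16.1, specify an overall per-subject row over Doses 1 and 2, in all groups, as the row for display between groups. Apply it to the individual solicited symptoms, the local, general and any-AE rows, the 30-day unsolicited tables and the concomitant-medication rows (also SAP 13). State that it applies to both the second interim and the final tables.

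Make the Dose 3 and over-three-doses summaries mandatory in the Subcohort Exposed Set, and name that set in SAP 16.1. Allow those tables at the second interim under SAP 4.3.

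The all-doses row need not be removed, since the primary objective covers the entire study period. If it is kept, label it as based on unequal numbers of doses and not for comparison with placebo.

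The cost is a wording change and one extra set of tables. No new data are needed and study conduct does not change.

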9.4.2.2 Internal Safety Review Committee Evaluations

At each iSRC timepoint, a blinded review will be done by the GSK Safety Review Team (SRT) followed by an unblinded review of safety data by the iSRC. No individual clinical study report (CSR) will be written as a result of these safety evaluations.

If there are any safety concerns observed during SRT reviews post Dose 3, an ad hoc iSRC meeting will take place to review the unblinded safety data.

9.4.3 Analysis of Immunogenicity

The primary analysis will be based on the Per-protocol Set for analysis of immunogenicity. If, in any study group, the percentage of vaccinated subjects with serological results excluded from the Per-protocol Set for analysis of immunogenicity is 10% or more, a second analysis based on the Full Analysis Set will be performed.

9.4.3.1 Within Group Assessment

For each study group, at each timepoint that blood samples are collected for humoral immune response and for each assay:

[figure not shown]
- Percentage of subjects above the assay cutoff with their exact 95% CI will be tabulated.
- Geometric mean concentrations/geometric mean titers and their 95% CI will be calculated.
- Geometric mean fold-rise with their exact 95% CI will be tabulated.

For each study group, at each blood sampling timepoint for humoral immune response after vaccination, and for each assay:

- Antibody concentrations/titers will be investigated using Reverse Cumulative Curves.

9.4.3.2 *Between Groups Assessment*

CCI

9.4.4 Missing Data

Data from subjects who withdraw from the study, including AEs and any follow-up, will be included in the analyses of primary and secondary outcomes. Missing data will not be imputed.

9.5 Interim Analyses

A first interim analysis will be performed when all data up to 1 month after Dose 2, ie, Day 61 (ie, data that are as clean as possible) are available. The immunogenicity data available until Day 61, and the safety and reactogenicity data available at the time of this analysis will be described.

Second interim analysis will be performed when all data up to 1 month after Dose 3, ie, Day 521 (ie, data that are as clean as possible) are available. The immunogenicity data available until Day 521, and the safety and reactogenicity data available at the time of this analysis will be described.

All analyses are descriptive and with the aim to characterize the safety, reactogenicity, and immunogenicity data and therefore no statistical adjustment for interim analysis is required (refer to Section 9.8).

